2.3 Exploratory Objectives

1. To assess changes in cell free DNA mutation profile, including mutations in TP53, PIK3CA, ESR1, and RB1 and their correlation with treatment response.
2. To correlate archival tumor mutation profile and RB protein status with treatment response.
3. To assess intrinsic and acquired resistance mechanisms to palbociclib in tumor samples collected at baseline and at progression.
4. To assess changes in serum thymidine kinase activity and correlate with treatment response and absolute neutrophil count.
5. To establish patient derived xenograft (PDX) models from tumor biopsies before treatment and at progression for future studies.
6. To assess baseline and changes in Circulating Tumor Cell (CTC) gene expression profiles and to correlate with treatment response.

3.0 PATIENT SELECTION

3.1 Inclusion Criteria

1. Histologically confirmed metastatic ER+ and/or PR+ and HER2- breast cancer who are candidates for palbociclib in combination with either letrozole or fulvestrant per treating physician.
2. Presence of measurable or non-measurable disease by RECIST 1.1 criteria.
3. One prior systemic therapy in the metastatic setting is allowed, but patients who have not had any prior systemic therapies in the metastatic setting are also eligible.
 - Note: patients who were started on endocrine therapy monotherapy as their 1st line or 2nd line systemic therapy in the metastatic setting for no more than 28 days and without clinical progression prior to the initiation of the study drug therapy are allowed to enroll on the study as their 1st line or 2nd line therapy, respectively.
4. At least 18 years of age.
5. ECOG performance status ≤ 2 (see Appendix A)

6. Normal bone marrow and organ function as defined below:
 - a. Absolute neutrophil count $\geq 1,500/\text{mcl}$
 - b. Platelets $\geq 100,000/\text{mcl}$
 - c. Total bilirubin $\leq \text{IULN}$ or total bilirubin $\leq 3.0 \times \text{IULN}$ with direct bilirubin within normal range in patients with documented Gilbert's syndrome
 - d. AST(SGOT)/ALT(SGPT) $\leq 1.5 \times \text{IULN}$ (up to $5 \times \text{IULN}$ in patients with liver disease)
 - e. Creatinine $\leq \text{IULN}$ OR creatinine clearance $\geq 60 \text{ mL/min/1.73 m}^2$ for patients with serum creatinine levels above institutional normal (IULN) (calculated by Creatinine Clearance Estimate by Cockcroft-Gault Equation)
7. Pre- or post-menopausal women are allowed. If pre- or peri-menopausal, concurrent ovarian suppression for pre- or peri-menopausal women is required.
8. Women of childbearing potential must agree to use adequate contraception (hormonal or barrier method of birth control, abstinence) prior to study entry and for the duration of study participation. Should a woman become pregnant or suspect she is pregnant while participating in this study, she must inform her treating physician immediately.
9. Able to swallow and retain oral medication.
10. Washout of at least 3 weeks from prior chemotherapy or targeted therapy that induces myelosuppression and recovery of treatment related adverse events to grade 1 or less, with the exception of alopecia, is required prior to the start of palbociclib.
11. Ability to understand and willingness to sign an IRB approved written informed consent document (or that of legally authorized representative, if applicable).

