3.2 Exclusion Criteria

1. Prior therapy with any CDK inhibitor.
2. Currently receiving any other investigational agents.
3. Currently receiving exogenous estrogen replacement therapy (topical vaginal estrogen therapy is allowed).
4. Known brain metastases. Patients with known brain metastases must be excluded from this clinical trial because of their poor prognosis which could affect the evaluation of all-cycle adverse events.
5. A history of allergic reactions attributed to compounds of similar chemical or biologic composition to palbociclib or other agents used in the study.
6. Receiving any medications or substances that are potent inhibitors or inducers of CYP3A isoenzymes within 7 days prior to registration.

7. Clinically significant history of liver disease.
8. A condition that would interfere with enteric absorption.
9. Uncontrolled intercurrent illness including, but not limited to, ongoing or active infection, symptomatic congestive heart failure, unstable angina pectoris, or cardiac arrhythmia.
10. Pregnant and/or breastfeeding. Women of childbearing potential must have a negative pregnancy test within 7 days of study entry.
11. Known HIV-positivity on combination antiretroviral therapy because of the potential for pharmacokinetic interactions with palbociclib. In addition, these patients are at increased risk of lethal infections when treated with marrow-suppressive therapy. Appropriate studies will be undertaken in patients receiving combination antiretroviral therapy when indicated.

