5.0 TREATMENT PLAN

5.1 Agent Administration

Agent	Dose	Route	Schedule	Cycle Length
Palbociclib	125 mg	PO	5 days on and 2 days off, starting C1D1	28 days (4 weeks)
Letrozole*	2.5 mg	PO	Daily	
Fulvestrant*	500 mg	IM	Every 14 days for the first 3 doses followed by every 28 days	
Goserelin**	3.6 mg	SC	Every 28 days (Day 1 of each cycle)	
* Letrozole OR fulvestrant will be administered with palbociclib per physician choice. ** Only if pre- or peri-menopausal				

Patients will be instructed to make use of medication diaries (Appendices B and C) to act as records of administration for palbociclib and letrozole (if applicable).

Palbociclib at a dose of 125 mg should be taken by mouth with food on a 5 days on/2 days off schedule (meaning: on Days 1-5, 8-12, 15-19, and 22-26 of each 28-day cycle). If a patient misses a day's dose entirely, she must be instructed not to make it up the next day but just take her regular dose at the next assigned time. If a patient vomits any time after taking a dose, she must be instructed not to retake the dose but resume subsequent dosing at the next assigned time. If a patient inadvertently takes an extra dose during a day, she must be instructed to not take the next day's dose.

Patients who have been on stable doses of palbociclib for 6 consecutive cycles can be assessed for retreatment every 2 or 3 cycles to coincide with imaging. These patients must meet retreatment criteria (as described in Section 6.4) and will have labs drawn for retreatment (CBC with differential and CMP) and correlative studies (serum, plasma, cell-free DNA, and circulating tumor cells) to correspond with imaging studies that take place every 2-3 cycles. This allows patients on stable doses of palbociclib to return to clinic for retreatment at greater intervals.

Patients who are receiving letrozole will take it daily by mouth, every day of each 28-day cycle, at a dose of 2.5 mg. If a patient misses a day's dose entirely, she must be instructed not to make it up the next day but just take her regular dose on the next day. If a patient vomits any time after taking a dose, she must be instructed not to retake the dose but resume subsequent dosing on the next day. If a patient inadvertently takes an extra dose during a day, she must be instructed to not take the next day's dose.

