5.3 General Concomitant Medication and Supportive Care Guidelines

While taking palbociclib, patients should be instructed to avoid food or drugs that are known strong CYP3A4 inhibitors or inducers, including grapefruit and grapefruit juice. Please refer to Appendix D for a list of prohibited medications.

No specific antidotes exist for the treatment of palbociclib overdose. Since renal excretion of palbociclib is minimal, the benefit of hemodialysis in the treatment of a palbociclib overdose is probably negligible. The treatment of overdose of palbociclib should consist of general supportive measures. If indicated, elimination of unabsorbed drug should be achieved by emesis or gastric lavage.

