8.2.7 Potential Drug Interactions

Letrozole is generally safe to administer with other medicines. However, concomitant use of agents and herbal products that alter ER function are specifically not allowed.

For further information, please refer to the FDA-approved package insert for letrozole.

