8.3.7 Potential Drug Interactions

There are no known drug-drug interactions.

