APPENDIX D: List of CYP3A4 Strong Inhibitors and Inducers
(<http://medicine.iupui.edu/clinpharm/ddis/clinical-table/>)

Inhibitors

Indinavir
Nelfinavir
Ritonavir
Clarithromycin
Itraconazole
Ketoconazole
Nefazodone
Lopinavir
Posaconazole
Saquinavir
Telaprevir
Telithromycin
Voriconazole
Grapefruit and grapefruit juice

Inducers

Carbamazepine
Efavirenz
Nevirapine
Phenobarbital
Phenytoin
Pioglitazone
Rifabutin
Rifampin
St. John's Wort
Troglitazone

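### Inclusion 8 accepts hormonal birth control without excluding systemic estrogen: no visible rule bars it with fulvestrant, and the letrozole rule that probably does is not cross-referenced

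*Combined protocol and SAP*

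**What the plan says.** Section 3.1, item 8, requires women of childbearing potential to agree to "adequate contraception (hormonal or barrier method of birth control, abstinence) prior to study entry and for the duration of study participation". Item 7 of the same section admits pre- and post-menopausal women and adds that "concurrent ovarian suppression for pre- or peri-menopausal women is required". The treatment table in section 5.1 lists goserelin with the note "Only if pre- or peri-menopausal".

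The provisions that might limit the contraceptive are spread over several sections:

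- Section 3.2, exclusion 3: "Currently receiving exogenous estrogen replacement therapy (topical vaginal estrogen therapy is allowed").
- Section 5.3: "patients should be instructed to avoid food or drugs that are known strong CYP3A4 inhibitors or inducers". It sends the reader to "APPENDIX D: List of CYP3A4 Strong Inhibitors and Inducers" for the prohibited drugs.
- Section 5.4: two acceptable methods are needed, one of them a barrier. Nothing is said about the type of the other.
- Section 8.1.9: what counts as effective contraception is left to the judgment of the principal investigator or a designated associate.
- Section 8.2.7 (letrozole): "concomitant use of agents and herbal products that alter ER function are specifically not allowed".
- Section 8.3.7 (fulvestrant): "There are no known drug-drug interactions".

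**The concern.** The trial treats hormone-receptor-positive cancer by blocking estrogen signaling, yet its eligibility text names hormonal birth control as adequate and does not separate estrogen-containing products from the rest.

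The plan's own pharmacology shows why that matters. Section 8.2.2 describes letrozole as lowering the body's production of estrogen, which does nothing about estrogen taken as a drug. Section 8.3.2 describes fulvestrant as a competitive antagonist whose receptor affinity is similar to estradiol's, so added estrogen would compete with it. The women to whom a contraception rule applies largely overlap with those who must have ovarian suppression under item 7, and systemic estrogen would work against that too.

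What is at stake is mainly patient protection. If any woman were exposed, her progression-free survival, response and clinical benefit could in principle be affected. These are secondary endpoints that section 15.3 plans to estimate with confidence intervals, and section 15 sets no hypothesis test for them.

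**Working it through.** No arithmetic applies: the plan states no figure on this point, and none can be derived. The check is to take a woman of childbearing potential who uses an estrogen-containing contraceptive and ask which rule in the text would stop her, first on fulvestrant and then on letrozole.

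**On fulvestrant**

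1. Inclusion 8 does not stop her. A product of this kind falls under *hormonal* in its ordinary sense.
2. Exclusion 3 does not stop her on its wording. It is limited to estrogen replacement, and contraception is not replacement. It is also worded as a test of current use at entry, not as a ban for the rest of the study.
3. Section 5.3 and Appendix D do not stop her. They deal only with strong CYP3A4 inhibitors and inducers, and no contraceptive is on the list.
4. Section 5.4 adds a barrier method but leaves the second method open. A hormonal product can therefore be the second method, though not the only one.
5. Section 8.1.9 allows an investigator to refuse the product but does not require it.
6. Section 8.3.7 states no restriction. Unlike the letrozole and goserelin sections (8.2.7 and 8.4.6), it does not refer to a package insert.

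Result: no visible rule bars the product.

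**On letrozole**

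Steps 1 to 5 are the same. Section 8.2.7 then adds its ban on agents that alter ER function. The phrase is not defined. Estrogen is the receptor's own ligand, so the natural reading is that it is covered. The ban sits in a drug-information section, however, and inclusion 8 does not refer to it. A coordinator working from the eligibility list sees only that hormonal methods are adequate.

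Result: probably barred, but not from the place where the decision is made.

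**How many women**

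The plan gives neither an expected number of women of childbearing potential nor any figure for contraceptive use. The lower bound is 0 and no upper bound can be set from the text, so no effect on any secondary endpoint can be calculated. The primary endpoint is severe toxicity within 29 days, tested with 47 patients and a threshold of 24 patients without an event. The argument here concerns loss of anti-estrogen effect, so it does not bear on that endpoint, the threshold or the sample size.

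**The case against.** The strongest reply has four parts.

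- *The two rules do not conflict.* Inclusion 8 lists acceptable categories and does not require or recommend estrogen. A site can meet both inclusion 8 and section 8.2.7 with a barrier, abstinence or an estrogen-free hormonal method. **This stands.** A reader might infer that the protocol contradicts itself for letrozole patients, but the documents do not support that. They show a general permission narrowed by a specific ban elsewhere. What is missing is the cross-reference.
- *A restriction may exist in text not seen here.* The available text has a gap between sections 8.1.9 and 8.2, at the end of the palbociclib section, and another within 8.1.3. Palbociclib is the one drug every patient takes, and it has no interaction subsection in the visible text. The package inserts named in 8.2.7 and 8.4.6 were also not available. **This stands as a limit.** The statement about fulvestrant patients covers visible text only. Even if a ban exists in the gap, inclusion 8 should be reworded to agree with it.
- *No oncologist would allow it.* The barrier requirement, the investigator's discretion and the exclusion of estrogen replacement all point the other way, and nothing in the documents suggests that exposure would occur. **This stands on frequency**, and is why the point is minor. It does not justify leaving an unqualified permission in the eligibility text of a multicenter trial.
- *The harm is inferred.* Sections 8.2.2 and 8.3.2 describe mechanisms and report no outcomes, and 8.3.2 also says that fulvestrant reduces the receptor protein, so competition is not its whole action. **This stands.** A reader might infer that progression-free survival, response or clinical benefit will be biased, but the documents give no exposure, dose or effect to support that.

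**Conclusion.** The point holds as a cheap improvement on a minor patient-safety matter. Inclusion 8 approves hormonal contraception for the whole study without excluding systemic estrogen, in patients whose treatment is meant to remove or block estrogen. On fulvestrant, no visible rule closes the gap. On letrozole, section 8.2.7 probably closes it, but the eligibility text does not say so.

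Its size is unknown and may be zero. The 29-day primary endpoint, the 24-of-47 rule and N = 47 are untouched.

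The conclusion rests on three assumptions: that *hormonal* has its ordinary meaning, which includes estrogen-containing products; that estrogen counts as an agent that alters ER function (for the letrozole part); and that the unseen text contains no study-wide ban (for the fulvestrant part).

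The argument concerns systemic estrogen only. It gives no ground to forbid estrogen-free hormonal methods or to question the exception for topical vaginal estrogen.

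**What to change.** Make two wording changes:

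1. In section 3.1, item 8, require that any contraceptive used be free of systemic estrogen.
2. In section 5.3, state once that systemic exogenous estrogen, including estrogen-containing contraceptives, is not allowed while on study, whether the partner is letrozole or fulvestrant, and that topical vaginal estrogen remains permitted.

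The second method in section 5.4 is then limited by the section 5.3 rule and needs no separate list. Section 8.2.7 can stay as it is, because the eligibility and concomitant-medication text will no longer depend on how its undefined phrase is read.

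The cost is a short amendment and a slightly narrower choice of contraceptive. The sample size, endpoints and analysis do not change.

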3.2 Exclusion Criteria

1. Prior therapy with any CDK inhibitor.
2. Currently receiving any other investigational agents.
3. Currently receiving exogenous estrogen replacement therapy (topical vaginal estrogen therapy is allowed).
4. Known brain metastases. Patients with known brain metastases must be excluded from this clinical trial because of their poor prognosis which could affect the evaluation of all-cycle adverse events.
5. A history of allergic reactions attributed to compounds of similar chemical or biologic composition to palbociclib or other agents used in the study.
6. Receiving any medications or substances that are potent inhibitors or inducers of CYP3A isoenzymes within 7 days prior to registration.

7. Clinically significant history of liver disease.
8. A condition that would interfere with enteric absorption.
9. Uncontrolled intercurrent illness including, but not limited to, ongoing or active infection, symptomatic congestive heart failure, unstable angina pectoris, or cardiac arrhythmia.
10. Pregnant and/or breastfeeding. Women of childbearing potential must have a negative pregnancy test within 7 days of study entry.
11. Known HIV-positivity on combination antiretroviral therapy because of the potential for pharmacokinetic interactions with palbociclib. In addition, these patients are at increased risk of lethal infections when treated with marrow-suppressive therapy. Appropriate studies will be undertaken in patients receiving combination antiretroviral therapy when indicated.

3.3 Inclusion of Women and Minorities

Women and members of all races and ethnic groups are eligible for this trial. Enrollment will be restricted to women as breast cancer occurs primarily in women.

4.0 REGISTRATION PROCEDURES

Patients must not start any protocol intervention prior to registration through the Siteman Cancer Center.

The following steps must be taken before registering patients to this study:

1. Confirmation of patient eligibility by Washington University
2. Registration of patient in the Siteman Cancer Center OnCore database
3. Assignment of unique patient number (UPN)

Once the patient has been entered in the Siteman Cancer Center OnCore database, the WUSM coordinator will forward verification of enrollment and the UPN via email.

4.1 Confirmation of Patient Eligibility

Confirm patient eligibility by collecting the information listed below and scanning and emailing it to the research coordinator listed in the *Siteman Cancer Center Clinical Trials Core Protocol Procedures for Secondary Sites* packet at least one business day prior to registering patient:

1. Your name and contact information (telephone number, fax number, and email address)
2. Your site PI's name, the registering MD's name, and your institution name
3. Patient's race, sex, and DOB
4. Three letters (or two letters and a dash) for the patient's initials
5. Currently approved protocol version date
6. Copy of signed consent form (patient name may be blacked out)
7. Planned date of enrollment
8. Completed eligibility checklist, signed and dated by a member of the study team
9. Copy of appropriate source documentation confirming patient eligibility

4.2 Patient Registration in the Siteman Cancer Center OnCore Database

Registrations may be submitted Monday through Friday between 8am and 5pm CT. Urgent late afternoon or early morning enrollments should be planned in advance and coordinated with the Washington University research coordinator. Registration will be confirmed by the research coordinator or his/her delegate by email within one business day. Verification of eligibility and registration should be kept in the patient chart.

All patients at all sites must be registered through the Siteman Cancer Center OnCore database at Washington University.

4.3 Assignment of UPN

Each patient will be identified with a unique patient number (UPN) for this study. Patients will also be identified by first, middle, and last initials. If the patient has no middle initial, a dash will be used on the case report forms (CRFs). All data will be recorded with this identification number on the appropriate CRFs.

5.0 TREATMENT PLAN

5.1 Agent Administration

Agent	Dose	Route	Schedule	Cycle Length
Palbociclib	125 mg	PO	5 days on and 2 days off, starting C1D1	28 days (4 weeks)
Letrozole*	2.5 mg	PO	Daily	
Fulvestrant*	500 mg	IM	Every 14 days for the first 3 doses followed by every 28 days	
Goserelin**	3.6 mg	SC	Every 28 days (Day 1 of each cycle)	
* Letrozole OR fulvestrant will be administered with palbociclib per physician choice. ** Only if pre- or peri-menopausal				

Patients will be instructed to make use of medication diaries (Appendices B and C) to act as records of administration for palbociclib and letrozole (if applicable).

Palbociclib at a dose of 125 mg should be taken by mouth with food on a 5 days on/2 days off schedule (meaning: on Days 1-5, 8-12, 15-19, and 22-26 of each 28-day cycle). If a patient misses a day's dose entirely, she must be instructed not to make it up the next day but just take her regular dose at the next assigned time. If a patient vomits any time after taking a dose, she must be instructed not to retake the dose but resume subsequent dosing at the next assigned time. If a patient inadvertently takes an extra dose during a day, she must be instructed to not take the next day's dose.

Patients who have been on stable doses of palbociclib for 6 consecutive cycles can be assessed for retreatment every 2 or 3 cycles to coincide with imaging. These patients must meet retreatment criteria (as described in Section 6.4) and will have labs drawn for retreatment (CBC with differential and CMP) and correlative studies (serum, plasma, cell-free DNA, and circulating tumor cells) to correspond with imaging studies that take place every 2-3 cycles. This allows patients on stable doses of palbociclib to return to clinic for retreatment at greater intervals.

Patients who are receiving letrozole will take it daily by mouth, every day of each 28-day cycle, at a dose of 2.5 mg. If a patient misses a day's dose entirely, she must be instructed not to make it up the next day but just take her regular dose on the next day. If a patient vomits any time after taking a dose, she must be instructed not to retake the dose but resume subsequent dosing on the next day. If a patient inadvertently takes an extra dose during a day, she must be instructed to not take the next day's dose.

Patients who are receiving fulvestrant will receive it at a dose of 500 mg as two 5 mL intramuscular injections (one into each buttock) on Days 1 and 15 of Cycle 1 and then on Day 1 of each cycle thereafter.

Goserelin is given as a subcutaneous injection every 28 days. It is preferred to be given on Day 1 of each cycle, but it may be administered on any day of the treatment cycle to accommodate its specific Q28-day cycle. It will be given to pre- and peri-menopausal women only.

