2.2 Secondary Objectives

1. To determine the rate of grade 3 or higher neutropenia in patients with hormone receptor positive breast cancer treated with palbociclib on a 5 days on/2 days off schedule during all cycles.
2. To determine the rate of palbociclib dose reduction, interruption, or discontinuation.
3. To determine the adverse events profile of palbociclib given on a 5 days on/2 days off schedule.
4. To determine the progression free survival in patients with hormone receptor positive breast cancer treated with palbociclib on a 5 days on/2 days off schedule.
5. To determine the overall response rate (CR+PR) in patients with hormone receptor positive breast cancer treated with palbociclib on a 5 days on/2 days off schedule.
6. To determine the clinical benefit rate (CR+PR+SD for at least 6 months) in patients with hormone receptor positive breast cancer treated with palbociclib on a 5 days on/2 days off schedule.

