6.3 Dose Modifications for Palbociclib

Patients will be monitored for toxicity and the dose of palbociclib may be adjusted as indicated in the dose modification table below.

Dose Level	Palbociclib 5 Days On / 2 Days Off
1 (starting dose)	125 mg/day
-1	100 mg/day
-2	75 mg/day
Note that palbociclib dose reduction below 75 mg/day is not allowed	

Dose reduction by 1 and, if needed, 2 dose levels will be allowed depending on the type and severity of toxicity encountered. Patients requiring more than 2 dose reductions will be discontinued from the study.

Recommended dose reductions for palbociclib are detailed in the table below. Doses may be held as needed for toxicity resolution during a cycle. Doses omitted for toxicity are not replaced or restored within the same cycle (meaning that the cycle remains 28 days regardless of the number of doses of taken).

Treatment with palbociclib should be permanently discontinued if toxicity has not recovered to grade ≤ 2 within two weeks.

Palbociclib Dose Modifications Based on Worst Treatment-Related Toxicity in the Previous Cycle

Worst Toxicity During Previous Cycle	New Dose Level
Grade 4 neutropenia	Decrease by one dose level
Grade 4 thrombocytopenia	Decrease by one dose level
Grade 3 neutropenia associated with a documented infection or fever ≥ 38.5 °C	Decrease by one dose level
Grade ≥ 3 non-hematologic toxicity (includes nausea, vomiting, and diarrhea only if persisting despite maximal medical treatment)	Decrease by one dose level
Delay by > 1 week in receiving the next scheduled dose due to persisting treatment-related toxicities	If recovery occurs within 2 weeks, continue and decrease by one dose level
Inability to deliver at least 80% of the planned dose of PD 0332991 due to adverse events possibly related to study treatment	Decrease by one dose level

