6.4 Re-Treatment Criteria

A new cycle of treatment with palbociclib may begin only if:

- ANC \geq 1,000/mcL.
- Platelet count \geq 50,000/mcL.
- Non-hematologic toxicities have returned to baseline or Grade \leq 1 severity (or, at the investigator's discretion, Grade \leq 2 if not considered a safety risk for the patient).

Criteria for dose interruption within cycle:

- ANC $<$ 500/mcL.
- Platelet count $<$ 50,000/mcL.

Re-treatment within the cycle may only be started when ANC \geq 500/mcL and platelet count \geq 50,000/mcL.

Doses omitted for toxicity within a cycle are not replaced or restored within the same cycle (meaning that the cycle remains 28 days regardless of the number of doses of taken).

If these conditions are not met, hormone therapy may be continued but treatment with palbociclib must be delayed by one week. If, after a one-week delay, all toxicities have recovered within the limits described above, treatment with palbociclib can be resumed.

If the patient has not recovered after 2 weeks despite dose reduction to the lowest dose level, treatment with palbociclib will be permanently discontinued.

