10.0 STUDY CALENDAR

Screening/baseline evaluations are to be conducted within 2 weeks prior to start of protocol therapy. Scans and x-rays must be done no more than 4 weeks prior to the start of the protocol therapy. There is a +/-3 day window around each study visit.

	Screening	Baseline	Day 1 of each cycle ⁸	C1D15	C2D1	C2D15	End of every 2 nd or 3 rd cycle ⁸	Time of progression	30 day f/u
Informed consent	X								
H&P, ECOG PS	X		X		X			X	
CBC w/diff	X		X	X	X	X			
CMP	X		X		X				
β-hCG ¹	X								
Imaging	X						X	X	
Palbociclib			Given on a 5 days on / 2 days off schedule for each 28-day cycle						
Fulvestrant ³			X	X	X				
Letrozole ³			Daily						
Goserelin ⁴			X		X				
Medication diary			Daily, to be returned at the end of each cycle						
AE assessment			X -----X						
Archival Tissue		X ⁷							
Research biopsy (optional)		X						X	
Blood for serum		X		X ⁵	X ⁵		X ^{2,5}	X	
Blood for plasma		X		X ⁵	X ⁵		X ^{2,5}	X	
Blood for cfDNA		X		X ⁵	X ⁵		X ^{2,5}	X	
Blood for germline DNA		X							
Blood for circulating tumor cells		X			X		X ⁶	X	

1. Women of childbearing potential only
2. Beginning with the end of Cycle 2 but to coincide with imaging studies
3. Either fulvestrant OR letrozole will be given (MD decision)
4. Goserelin will be given to premenopausal women only
5. Instruct patient take palbociclib/hormonal therapy after blood draw, meaning blood draw needs to happen prior to the day's treatment.
6. Post 2 or 3 months after start of therapy (to coincide with ONLY the 1st imaging assessment of tumor response)
7. Archival tissue should include both primary and metastatic tissue
8. Labs and office visits could be reduced in frequency to q2-3 cycles to coincide with tumor imaging studies in patients on stable doses of palbociclib for at least 6 consecutive cycle

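### The optional two- to three-cycle CBC interval after six stable cycles leaves later cycle starts without the count that Section 6.4 requires, so the all-cycle grade 3+ neutropenia rate will read low

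*Combined protocol and SAP*

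**What the plan says.** - **Start condition.** Section 6.4: "A new cycle of treatment with palbociclib may begin only if" ANC is at least 1,000/mcL, platelets are at least 50,000/mcL and non-hematologic toxicity has recovered. No group of patients is exempt.
- **Reduced schedule.** Section 5.1: after six consecutive cycles on a stable dose, patients "can be assessed for retreatment every 2 or 3 cycles to coincide with imaging". The retreatment CBC and chemistry are drawn "to correspond with imaging studies that take place every 2-3 cycles". The same paragraph keeps the 6.4 conditions in force: "These patients must meet retreatment criteria (as described in Section 6.4").
- **Calendar, footnote 8.** "Labs and office visits could be reduced in frequency to q2-3 cycles to coincide with tumor imaging studies", again for patients with at least six stable-dose cycles.
- **Section 11, footnote 1.** At the physician's discretion these patients may be dosed at two- to three-cycle intervals, with treatment forms completed to match.
- **Objectives.** Secondary objective 1 in Section 2.2 is the rate of grade 3 or higher neutropenia in patients "treated with palbociclib on a 5 days on/2 days off schedule during all cycles". Objective 2 is the rate of dose reduction, interruption or discontinuation.
- **Grade boundary.** The table in Section 1.3 places grade 3 ANC below 1,000 and down to 500/mm³.
- **Dose table.** In Section 6.3 the grade 3 row for neutropenia reads "Grade 3 neutropenia associated with a documented infection or fever". Uncomplicated grade 3 neutropenia has no row of its own.
- **Analysis.** Section 15.3 gives the AE rate with a 95% CI and does not say how cycles without a count are handled.

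**The concern.** Section 6.4 sets a condition for every cycle. Section 5.1 repeats that it must be met but schedules the test that would show it only every second or third cycle. A site using the reduced schedule has no scheduled way to confirm the condition for the cycles in between.

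This is also a measurement problem. The ANC that permits a cycle to start is the boundary between grade 2 and grade 3, so the omitted count is the one that detects the endpoint of objective 1. The toxicity form is continuous, but it cannot record a silent low count that was never drawn.

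A stable dose does not identify patients free of neutropenia. Uncomplicated grade 3 counts do not by themselves reduce the dose under Section 6.3, so a patient with such counts can qualify for the reduced schedule.

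The error runs in one direction. Fewer counts mean fewer recorded events and fewer count-driven delays in the patients who stay longest on treatment. Less high-grade neutropenia and less interruption are what Section 1.3 hypothesizes for the new schedule.

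**Working it through.** **1. The plan's own figure.** Section 15.2 tests 0.38 against 0.60 for the proportion without an event, with N = 47 and success at 24 or more. The exact binomial gives:

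- P(X ≥ 24 | 47, 0.38) = 0.0466, printed as 4.7%
- P(X ≥ 24 | 47, 0.60) = 0.9181, printed as 91.8%

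Both reproduce. The primary window is the first 29 days, with calendar CBCs at C1D15 and C2D1, well before any reduced schedule.

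**2. First start without a count.** The calendar images at the end of every second or third cycle. Section 12.1 says every 12 weeks, which is 84/28 = 3 cycles. Six is a multiple of both 2 and 3, so the end of Cycle 6 is an imaging and laboratory point either way, and that count serves the start of Cycle 7. The next count serves Cycle 9 (every two) or Cycle 10 (every three). The first uncounted start is therefore Cycle 8, or later if a dose change delays six consecutive stable cycles.

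**3. Share of starts without a count.**

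| Starts | CBC each cycle | Every 2 | Every 3 |
|---|---|---|---|
| Cycles 7–12 (6) | 6 counted | 3 counted, 3 not | 2 counted, 4 not |
| Cycles 7–18 (12) | 12 counted | 6 counted, 6 not | 4 counted, 8 not |
| Cycles 7–24 (18) | 18 counted | 9 counted, 9 not | 6 counted, 12 not |
| Uncounted | 0% | 50% | 66.7% |

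**4. Effect on a per-patient all-cycle rate (illustration).** Let *a* be the proportion with an event by Cycle 6, *h* the risk of a grade 3+ count at each later start, and *m* the number of counts over Cycles 7–12. The recorded rate is

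R(m) = a + (1 − a)[1 − (1 − h)^m].

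The documents give neither *a* nor *h*; both are assumed. The formula also assumes independent risks, and that every patient event-free at Cycle 6 remains on treatment and uses the reduced schedule through Cycle 12.

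With a = 0.50 and h = 0.05:

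- m = 6: 0.50 + 0.50 × (1 − 0.95⁶) = 0.50 + 0.50 × 0.265 = 63.2%
- m = 3: 0.50 + 0.50 × 0.143 = 57.1%
- m = 2: 0.50 + 0.50 × 0.098 = 54.9%

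| a | h | Each cycle | Every 2 | Every 3 |
|---|---|---|---|---|
| 50% | 2% | 55.7% | 52.9% | 52.0% |
| 50% | 5% | 63.2% | 57.1% | 54.9% |
| 50% | 10% | 73.4% | 63.5% | 59.5% |
| 50% | 20% | 86.9% | 74.4% | 68.0% |
| 40% | 5% | 55.9% | 48.6% | 45.9% |
| 62% | 5% | 72.1% | 67.4% | 65.7% |

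**5. If the rate were per cycle.** With equal risk at each start and uncounted cycles kept in the denominator, only 3/6 = 50% or 2/6 = 33% of Day 1 events over Cycles 7–12 would be recorded. Using counted cycles as the denominator removes that particular bias.

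**The case against.** **The rules can both be followed.** The reduced schedule is optional in all three places, and Section 5.1 keeps 6.4 in force. A site that draws a CBC every cycle satisfies everything. This stands: a reader might infer that the instructions are impossible to follow together, and they are not. But a site that takes the option is left with a condition it has no scheduled test to check.

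**Delays are recorded.** A reader might infer that interruptions go unobserved. The calendar has a daily palbociclib diary returned each cycle, so delays that occur are captured. What the schedule does is prevent a count-driven delay from arising. That lowers the rate in objective 2 without losing data on it. Objective 2 also does not name delays, and whether a late cycle start counts as an interruption is undefined.

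**Early events are already counted.** If objective 1 is per patient, which the documents do not define, someone with grade 3 counts in Cycles 1–6 is already an event. Only first events after the reduced schedule begins can be lost. Someone who runs low repeatedly may also be caught at the next scheduled count, so independence may overstate the loss.

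**Larger figures do not carry over.** One could take the PALOMA-2 median PFS of 24.8 months as 24.8 × 30.44/28 = 27 cycles and note that detection at 5% risk falls from 1 − 0.95²¹ = 66% to 1 − 0.95⁷ = 30% when counts are drawn every three cycles. That describes a patient with no earlier event over a first-line horizon. Section 15.2 expects 70% second-line patients, and the documents give no second-line PFS.

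**No comparison is at stake.** The all-cycle rate is descriptive, and the CBC schedules of the PALOMA trials are not in the documents, so a bias relative to those trials cannot be shown. This stands and limits the weight of the point.

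**Conclusion.** The point holds for patients placed on the reduced schedule. Sections 5.1, 10.0 (footnote 8) and 11 permit 50% or 66.7% of later cycle starts, normally from Cycle 8, to go without the count on which 6.4 makes each start depend. The all-cycle neutropenia rate is then a lower bound, and the schedule itself lowers the rate of count-driven interruption or delay.

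The base illustration is a shortfall of about 6 points (63.2% to 57.1%, every two cycles) or 8 points (63.2% to 54.9%, every three). With half the patients already counted, it ranges from about 3 to 4 points at 2% risk per start to 12 to 19 points at 20%. The sizes rest on the assumptions in the working and shrink as fewer patients take the option.

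A reader might infer that the main conclusion is compromised. It is not: the first-29-day endpoint and the rule of 24 of 47 are untouched. Nor would Cycles 1–6 be fully observed, because no mid-cycle count is scheduled for anyone after C2D15, so Cycles 3–6 are seen on Day 1 only. The amendment should be made, but the trial's primary test does not depend on it.

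**What to change.** 1. Reconcile Section 5.1, calendar footnote 8 and the Section 11 footnote with Section 6.4, so that the documents give one answer on whether a cycle may start without the ANC and platelet check. Which answer is a clinical decision for the sponsor; none is proposed here.
2. In Section 15.3, define whether objective 1 is per patient or per cycle, and whether a late cycle start counts as an interruption under objective 2.
3. Keep the all-cycle rate, since it is a stated objective. Add a table reporting objectives 1 and 2 separately for Cycles 1–6 (a Day 1 count scheduled in every cycle) and for later cycles, with the number of cycles that had a CBC as the denominator. State that the pooled rate is a lower bound, and note that Cycles 3–6 have Day 1 counts only.

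The reporting changes cost some protocol wording and one table, with no added patients or visits. The drawback is an all-cycle figure that looks less complete. Whether item 1 changes the number of blood draws depends on how the sponsor resolves it.
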